**Other Outcomes:**

1. Patient satisfaction with the VCE procedure. (Form Used: *CHEER #4*)

2. GI Physician Final Read and Site physician agreement of VCE results. (Form Used: *CHEER #5*)
3. Serious Adverse Events at Day 7 and Day 30 (Mortality, Re-Bleeding, Total Blood Transfusions, Surgery, Capsule-specific). (Form Used: *CHEER #7*)
4. ED Length of Stay (hours).
5. Hospital Length of Stay (days).
6. Cost-effective analysis.
  - At conclusion of study, we will construct a model using standard decision analysis software to examine the cost-effectiveness of three available strategies for a base-case patient who presents to the ED with either mild or moderate risk scenarios (by Glasgow-Blatchford Score) for requiring invasive hemostatic intervention (i.e., endoscopic, surgical, etc.) The three available diagnostic strategies are (1) direct imaging with video capsule endoscopy performed in the ED, (2) risk stratification using the Glasgow-Blatchford score, and, finally, (3) an admit-all strategy.

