### **8.7 Cheer 7: Patient Follow up**

This form is completed during the day 7 and day 30 follow up contact, please verify information via EHR if necessary.

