### **8.8 Cheer 8: Hospitalization Course/ Chart Review**

This form collects information on the hospitalization and procedures during the patient's hospital stay.

**8.9      Cheer 9: Adverse Event Form/ Serious Event  
From**

This form is completed if patient reports any AE or SAE's. Report to PI within 24 hours, SAE's are reported immediately.

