## **18.2 APPENDIX B – Document List**

Cheer 1: Screening Log

Cheer 2: Eligibility

Cheer 3: Patient Data Collection Form

Cheer 4: Patient Screening; GBS Score

Cheer 5: Patient Lab Values Pre- PillCam

Cheer 6: Patient Lab Values Post-PillCam

Cheer 7: Video Capsule Endoscopy Data Collection sheet

Cheer 8: EGD Data Collection Sheet

Cheer 9: Patient Satisfaction Day 7 and Day 30

Cheer 10: Patient Follow up Day 7 and Day 30

Cheer 11: Patient Chart Review

Cheer 12: Adverse Event Form/ Serious Event Form

Cheer 13: Protocol Deviation

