**Did you have an upper endoscopy after being discharged from the hospital? Yes No**

**What were the results of the endoscopy?**

Bleeding resolved

Bleeding persisted

New problem

Unsure

If patient has a new problem, please describe. \_\_\_\_\_

Did you have a return visit to the hospital? Yes No

Return date to the hospital? \_\_\_\_\_

Which Hospital? \_\_\_\_\_

Where you hospitalized for recurrent bleeding? \_\_\_\_\_

Did you have a second endoscopy? Yes No

What were the results? \_\_\_\_\_

When were you discharged? \_\_\_\_\_

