### 18.13 Patient Chart Review

## Patient Chart Review

Initials of person abstracting information from chart \_\_\_\_\_

Hospital discharge date \_\_\_\_\_

Blood transfusion? Yes No

Date of transfusion \_\_\_\_\_

Number of PRBC? \_\_\_\_\_

Additional endoscopy Yes No

How many? \_\_\_\_\_

Hemostatic therapy? Yes No

Surgery? Yes No

Date of surgery \_\_\_\_\_

Please describe surgery. \_\_\_\_\_

Disposition?

Home  
Rehabilitation  
Nursing home  
Deceased

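### Day 7 and Day 30 death, transfusion and surgery have no item on the follow-up form; outside a hospital stay they rest on patient-triggered reports and an optional record check, so ascertainment differs by setting and hence by arm

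*Combined protocol and SAP*

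**What the plan says.** Section 3.2 (Other Outcomes) lists "Serious Adverse Events at Day 7 and Day 30 (Mortality, Re-Bleeding, Total Blood Transfusions, Surgery, Capsule-specific" and gives the source as "Form Used: *CHEER #7". In section 8.7 that number is the follow-up form: "This form is completed during the day 7 and day 30 follow up contact, please verify information via EHR if necessary". In Appendix B the same number reads "Cheer 7: Video Capsule Endoscopy Data Collection sheet", and the follow-up form is Cheer 10.

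The printed follow-up form (18.12) covers symptoms, bleeding, loss of consciousness, gastroenterology visits, endoscopy and return visits, including "Where you hospitalized for recurrent bleeding". The chart review form (18.13) carries "Blood transfusion? Yes No", a transfusion date, red cell units, surgery with date, and a disposition that includes death. Section 8.8 describes its scope: "This form collects information on the hospitalization and procedures during the patient's hospital stay".

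Under section 8.9 the adverse event form is completed when the patient reports an event. Section 4.4 admits every Active Control subject and sends home CERA subjects who meet the discharge conditions. Section 11.3 compares categorical outcomes such as adverse events by study group with a chi-square test.

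**The concern.** Section 3.1 sets out to test whether capsule endoscopy can safely discharge low-risk patients, and section 2.3.1 counts a major outcome in a discharged patient as a potential major adverse event. A comparison of safety between arms needs each component looked for in the same way in both arms over the same 30 days. Here the structured fields for transfusion and surgery sit on a form tied to a hospital stay, and having an index stay is exactly what the randomised strategy changes. An event on day 2 in a control meets a dedicated field. The same event in a CERA subject at home must first be reported by the patient, or found in a record check that is not required. With 100 subjects and probably few events, one or two missed events could change the safety conclusion.

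**Working it through.** **1. Components against forms.** From the forms in the appendices and their descriptions in section 8:

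| Component | Follow-up call (18.12) | Chart review (18.13) | Adverse event form (18.14) |
|---|---|---|---|
| Death | none | disposition category | death item; fatal outcome |
| Re-bleeding | bleeding symptoms; admission for recurrence | no specific item | free text |
| Transfusion | none | yes/no, date, units | free text; generic intervention item |
| Surgery | none | yes/no, date, description | free text; generic intervention item |
| Capsule events | none | none | free text; relationship to capsule |
| Completed | Day 7 and Day 30 | for the hospital stay | when the patient reports an event |

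Of the five components, the named form has structured items for one, re-bleeding.

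**2. The plan's own figure.** The only computed design figure is power of at least 80% for a 25-point difference in admission among low-risk subjects (section 11.2). Inputs: 100 subjects, 20% high risk, so 80 low risk; 40 per arm (1:1 assumed, as the ratio is not stated); admission 100% against 75%; two-sided 0.05.
- Pooled proportion (1.00 + 0.75)/2 = 0.875; null SE = √(2 × 0.875 × 0.125/40) = 0.0740; alternative SE = √(0.75 × 0.25/40) = 0.0685.
- Power = Φ((0.25 − 1.96 × 0.0740)/0.0685) = Φ(1.53) ≈ 93.8%.

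The statement holds as a lower bound. The present point does not depend on it; it only supplies the discharge share for the low scenario below.

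**3. CERA subjects with no index stay (50 per arm assumed).**
- Low scenario, the design difference only: 0.25 × 40 = 10 (20% of 50).
- High scenario, the cited feasibility trial (section 2.1), with 7 of 37 admitted and so 30 of 37 sent home: 50 × 30/37 = 40.5, about 41 (81%).

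**4. How far the chart form covers controls.** The only stay length in the documents is a cited national median of 4.0 days (section 2.1). For a typical control that is 4/7 = 57% of the 7-day window and 4/30 = 13% of the 30-day window. Controls have the same gap after discharge.

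**5. Illustration of size.** Let q be the true 30-day event rate in both arms, s the share of events falling in the days when controls are inpatients, and h the share of CERA sent home. Suppose only the chart form captures events. Controls record 50·q·s, CERA records 50·(1 − h)·q·s, and the spurious difference is 50·q·s·h. All values of q and s are assumptions.

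| q | True events per arm | Difference at s = 4/30, h = 0.20 | Difference at s = 1, h = 30/37 |
|---|---|---|---|
| 2% | 1.0 | 0.03 | 0.81 |
| 5% | 2.5 | 0.07 | 2.03 |
| 10% | 5.0 | 0.13 | 4.05 |

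For given q, s and h these are upper limits. The other reporting routes will catch some events, and if capsule triage works, subjects sent home have fewer events than those admitted.

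**The case against.** A reader might infer that death, transfusion and surgery are recorded for all controls and not at all for CERA subjects sent home. The documents do not support that.

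- The adverse event form has a death item and a fatal outcome, and it is not limited by arm or setting. Section 10.2 applies serious event reporting to either group.
- The Day 7 and Day 30 contacts assess adverse events (section 4.4, item 14). Section 7.6 puts a list of questions at every contact, which includes surgical intervention and failure to pass the capsule.
- A transfusion or operation for bleeding would usually mean a return to hospital, and the call form asks about return visits, which hospital, and admission for recurrence. The EGD form allows an outpatient setting and records haemostasis.
- Controls are covered by the chart form only while they are inpatients.
- Nothing says the chart review is skipped for discharged CERA subjects or for readmissions; a readmission is also a hospital stay.
- Patients without reliable contact details are excluded (section 5.2), email and text are allowed (section 7.5), and loss to follow-up is reported to the DSMB (section 12.3).

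All of this stands, and it rules out the stronger reading. It does not close the gap. The adverse event form waits for the patient to report, which a subject who has died cannot do, and it has no field for units transfused. The section 7.6 list is framed as side effects of the study product, and the call form has no field for the answers on surgery or capsule passage. The record check applies only as "please verify information via EHR if necessary", and no step obtains records from another hospital named in the call.

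**Conclusion.** The point holds as one of uneven, partly unstructured ascertainment, not of absent data. Four of the five listed components have no item on the form named as their source, and that form's number means two different forms in the same document. In either arm, outside a hospital stay, death, transfusion and surgery rest on event-triggered reporting and an optional check. Total transfusions to Day 30 cannot be computed reliably for either arm from the printed forms.

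The difference between arms is concentrated in the days when controls are inpatients. It affects about 10 to 41 of 50 CERA subjects, assuming 1:1 allocation and depending on the discharge rate. The likely direction makes CERA look safer. The size is unknown: the illustration runs from almost nothing to about four events, on assumed event rates. This is a cheap improvement that should be made because safe discharge is the trial's stated aim.

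**What to change.** - Add to form 18.12, for both arms at Day 7 and Day 30: dated vital status with its source, transfusion (units), surgery, and capsule passage (not applicable where no capsule was given).
- State that form 18.13 is completed at Day 30 for every randomised subject. It should cover all hospital contacts from ED arrival to Day 30, with index-stay events recorded separately from later ones.
- In section 8.7, replace the optional check with a required record check for every subject, including those not reached. Request records from any other hospital named in the call.
- Correct the CHEER numbers so that section 3.2, section 8 and Appendix B agree.

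The cost is a form amendment, about 100 chart checks (one per subject) and a few outside record requests, all within the work of the existing coordinators.

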## 4 STUDY DESIGN

**4.1 Study Design:** Randomized Controlled Trial

**4.2 Proposed Sites:** GWU, Temple, Duke and other additional sites TBD.

**4.3 Patient Safety:** The study will be conducted in compliance with Declaration of Helsinki and ICH-GCP guidelines. Study design will be vetted by the local IRB at each participating institution prior to commencement.

**4.4 Study procedure:**

1. Screen potential patients with signs of upper GI bleeding (melena, h/o hematemesis or coffee-ground emesis) from general pool of ED patients. (Form used, *CHEER:1*)
2. Patients who screen as eligible will be approached about potential interest, to review of inclusion and exclusion criteria, and obtain informed consent. (*See below for full list of inclusion/ exclusion criteria.*)
3. Research Coordinator will calculate traditional risk stratification scores (Glasgow – Blatchford and Rockall).
4. All consented patients will be given a study ID and recorded in enrollment log. (Form used, *CHEER:2*)
5. Once enrolled, all subjects will be randomized to either Active Control (AC) [admission plus EGD within hospital stay] or experimental Capsule Endoscopy Risk Assessment (CERA) in ED.
6. Only patients randomized to the experimental arm will receive video capsule endoscopy in the emergency department. 20 to 60 minutes before capsule ingestion, each patient in the experimental arm receives a single dose of intravenous metoclopramide 10 mg (or erythromycin 500mg intravenously if there is a contraindication), which helps to promote gastric motility and improves visualization of the gastric mucosa at endoscopy. The Research Coordinator (RC) will prepare the patient for VCE. (*See below for description of procedure.*)
7. Within 2 hours of presenting to the ED, patient will ingest video capsule-- RC will monitor progress on real-time viewer for passage through pylorus. Upon passing the pylorus, we will record 5 more minutes of video or until battery runs out – whichever occurs first.
8. Patient data will be completed using a standardized data collection tool including the following elements: chief complaint of patient, history of present illness, past medical history, pertinent lab findings, current medications, vital signs, focused physical exam findings and all relevant treatments administered during the ED and hospital stay. (Form Used, *CHEER:3*)

9. At completion of VCE, patient satisfaction regarding VCE will be assessed in patients in the experimental group. (Form used, *CHEER*: 4)
10. For Active Control (AC) group each patient will be admitted.

During hospital admission, EGD will be performed on all subjects and hemostasis therapy applied as necessary. The study team decided against mandating that EGD be performed within 24 hours of hospital admission. This is a pragmatic trial. The longer the duration between the inpatient EGD and the ED VCE the greater the likelihood of discrepancy in the findings that may be due to a change in the lesion as part of its natural course or due to treatments delivered. However, the primary objective of the study is not to evaluate diagnostic accuracy of the ED VCE. The study team decided it was more important to enroll subjects in a timely manner than exclude subjects because the inpatient EGD was not completed within 24 hours.

For the experimental CERA group, subjects will be monitored for a minimum of 4 hours after ingestion. VCE will be undergo a formal review after completion of the VCE by a staff gastroenterologist with extensive experience in VCEs of the small bowel, colon, and esophagus. Both research personnel and the gastroenterologist will undergo a capsule training program organized by Medtronic and receive accreditation after the training.

11. Subjects in the experimental arm who have no sign of active bleeding, show no serious endoscopic findings on capsule, and have stable hemoglobin, blood pressure and heart rate for at least 4 hours will be discharged from the ED. Discharged CE patients will be scheduled to have an outpatient EGD within 3 days post discharge. Patients will be instructed to return to the ED sooner if signs of new bleeding develops. The Research Coordinator will facilitate setting up this appointment for the patient.

Any subject in the experimental arm with a positive VCE or a negative VCE but has a drop in Hemoglobin  $\geq 3$  at 4 hours or an elevated HR or low BP will be admitted. A hemoglobin drop between 2 and 3 will NOT automatically transfer patient to active control arm. In these cases, decision to proceed will be up to discretion of treating physician. We anticipate that all admitted patients in the experimental arm will undergo EGD in the hospital (same as AC arm.)

12. Primary Outcome: (1) Percent Discharged Home. Assumption is that 100% of Active Control / standard risk assessment will be admitted.
13. Secondary Outcome: Sensitivity and specificity of VCE compared to EGD
14. Safety outcomes. Patient will be followed for clinical course and EGD results. Day 7 and Day 30, subject follow-up by telephone (if home) or in person (if still in hospital) to assess for adverse events or recurrent bleeding episode. (Form Used, *CHEER*: 6,7)
15. All VCE's will be re-read by offsite gastroenterologists who are blinded to the first interpretation and the patient.

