The use of esophageal VCE in the ED to directly visualize the upper gastrointestinal tract and identify presence or absence of blood is a novel approach that has been studied in 4 ED-based studies. First, Rubin et al [14] studied 24 patients who presented to the ED with signs of UGIB. In this study, patients were randomized to either receive a VCE in the ED with real-time interpretation or receive standard care. Of the 12 patients in the experimental group, 7 had

bleeding detected on VCE and all had bleeding confirmed with subsequent EGD within 6 hours of hospital admission. Of the 4 patients who had a negative result on VCE (1 could not tolerate a VCE), all 4 had subsequent negative findings on EGD. On average, patients in the experimental group had an EGD performed sooner than the control group, but there was no change in clinical outcomes.

Gralnek et al [6] studied 41 patients who presented to the ED with UGIB and each received both a nasogastric tube and VCE. All patients had an EGD performed in the hospital within 12-24 hours after presentation. Of the 41 patients, 18 had blood in the upper gastrointestinal tract detected by EGD; capsule endoscopy detected blood in 83% (15/18) of these cases compared with a nasogastric aspiration, which detected blood in 33.3% (6/18). It is important to note that in 9 of these patients, the capsule detected blood in the duodenum, when nasogastric aspiration was reported to be either clear or bilious. Lack of detection of post-pyloric bleeding is an important limitation of nasogastric aspiration. Patients preferred VCE over nasogastric aspiration.

A third study conducted in the ED on the use of VCE enrolled 25 subjects with acute upper gastrointestinal hemorrhage [7]. In this study, [name] et al demonstrated an 88% sensitivity (95% CI: 65%- 100%) and 64% specificity (95% CI: 35%-92%) for the detection of fresh blood compared with an EGD performed with 24 hours. Capsule endoscopy missed a bleeding lesion located in the post- pyloric region, which was not imaged because of expired battery life (30 minutes).

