Most recently, the use of esophageal VCE in the ED was compared with the validated triage system, the Glasgow-Blatchford Score, to identify the number of patients who may be suitable for outpatient care [8]. Patients who presented to the ED for suspected acute UGIB were enrolled and administered esophageal VCE. For capsules that passed the pylorus and reached the duodenum, high-risk lesions were detected with a 95% sensitivity (95% CI: 72%-100%) and a 92% specificity (95% CI: 73%- 99%) compared with the Blatchford Score that demonstrated a 94% sensitivity (95% CI: 72%-100%) and a 16% specificity (95% CI: 5%-37%).

There has been one feasibility study published to test whether VCE can reduce hospital admissions in patients with suspected UGIB. In a prospective randomized controlled trial in which patients who presented with symptoms or signs suggestive of UGIB were randomized to receive either the standard treatment of hospital management versus VCE. Patients were also graded by Glasgow Blatchford score (GBS) at the ED for assessment of need of hospital admission. In this study, seventy-one patients fulfilled the recruitment criteria, with 37 subjects randomized to the VCE group and 34 subjects randomized to standard group. Seven VCE patients with active bleeding or significant endoscopic findings were admitted to the hospital compared with the standard group in which all 34 patients were admitted. There was no difference in the clinical outcome in terms of recurrent bleeding and 30-day mortality. In addition, hospital admission was also greatly reduced if VCE results were used instead of the GBS to determine whether patients were admitted or managed in the outpatient setting.[9]

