In all ED studies that have been conducted for acute upper gastrointestinal hemorrhage, VCE has performed well when it travels through the pylorus. However, several high-risk lesions were missed if the VCE did not travel through the pylorus before the battery expired. The time to pass the pylorus is variable. At 60 minutes, 98% of capsules visualize the duodenum [6]; when the battery life is only approximately 20-30 minutes, approximately 50% visualize the duodenum (12/25 [7], 44/83 [8], and 7/12 [14]). In one study, the single missed active bleeding occurred in a patient who was bleeding in the post-pyloric duodenum and in whom the VCE battery expired before reaching the post-pyloric region [7]. For standard EGD, the use of pro-kinetic agents such as erythromycin or metoclopramide has improved mucosal visualization and has been increasingly used before the procedure. This strategy, combined with 60 minutes of visualization, will likely increase the accuracy of VCE as well.

The cost of the VCE is an important factor that affects future use in the ED. The physician Medicare national average fee is \$705 for the PillCam UGI and \$50 for the professional fee. Although expensive, VCE may be cost-effective if it safely reduces hospital admissions or emergency EGD. For comparison, in 2011, 236,000 patients received an EGD (International Classification of Diseases, Ninth Revision code 45.13) in the hospital for an upper UGIB, the median length of stay was 4.0 days, and the median charges were \$23,549.17 [12].

A decision-analytic model showed that VCE is cost effective for low- to moderate-risk patients despite increased upfront costs compared with clinical decision rules or nasogastric tubes. The use of VCE in the ED can potentially lead to more patients being safely discharged from the ED. The hospital admission is the single most expensive decision made by an emergency physician. Chandran et al [8] showed that the higher sensitivity of VCE compared with the Glasgow-Blatchford Score would have saved \$1691 per VCE by increasing the number of patients who could receive an outpatient EGD.

Currently, the VCE does not replace the need for traditional EGD when hemostasis or biopsy is needed. Technological advancements may allow a VCE operator to control movement of the capsule, collect biopsy samples, and perform therapeutic functions.

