#### 3.2 Study Outcome Measures

3.2.1 Primary Outcome: (1) Percent Discharged Home. Assumption is that 100% of Active Control (AC) group will be admitted.

3.2.2 Secondary Outcome: Sensitivity and specificity of VCE compared to EGD. *Endpoints will be defined in the following way:*

Positive Video Capsule Endoscopy will be defined as:

1. Fresh blood or evidence of active bleeding visualized in upper GI tract.
2. Coffee ground blood visualized in upper GI tract, but no active bleeding seen.
3. A High Grade Non-Variceal Lesion (Forrest Ia, Ib, IIa or IIb).
4. Signs of Variceal Hemorrhage.
5. Signs of malignancy visualized in upper GI tract.

Negative VCE:

5. Clean stomach and duodenum, no fresh blood or coffee ground.
6. Upper GI pathology non-causative/ incidental.
7. A low grade non-Variceal lesion (Forrest IIc, III).

An Inconclusive VCE:

8. Any capsule that does not pass the pylorus before battery life is expired (and does not detect lesion in stomach or esophagus).

Positive EGD

1. Fresh blood or evidence of active bleeding.
2. Coffee ground but no active bleeding seen.
3. A High Grade Non-Variceal Lesion (Forrest Ia, Ib, IIa or IIb).
4. Signs of Variceal Hemorrhage.

Negative EGD

5. Clean stomach and duodenum, no fresh blood or coffee ground.
6. Upper GI pathology non-causative/ incidental.
7. A low grade non-variceal lesion (Forrest IIc, III).

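### Step 11 of section 4.4 gives no disposition for an Inconclusive capsule; read literally, it discharges a stable patient whose duodenum was never seen

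*Combined protocol and SAP*

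**What the plan says.** All references are to the combined protocol and SAP.

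- **Section 3.2.2** defines Positive, Negative and Inconclusive VCE. Inconclusive is "Any capsule that does not pass the pylorus before battery life is expired (and does not detect lesion in stomach or esophagus").
- **Section 4.4, step 11, discharge sentence.** The patients who go home are "Subjects in the experimental arm who have no sign of active bleeding, show no serious endoscopic findings on capsule, and have stable hemoglobin". The same sentence asks for steady pressure and pulse during a watch of 4 hours or longer. The wording is mandatory.
- **Section 4.4, step 11, admission sentence.** It covers "Any subject in the experimental arm with a positive VCE or a negative VCE but has a drop in Hemoglobin" of 3 or more, a raised heart rate or a low blood pressure. Physician discretion is given only for a hemoglobin drop between 2 and 3.
- **Section 2.1** says that "several high-risk lesions were missed if the VCE did not travel through the pylorus before the battery expired". It describes one missed post-pyloric bleeding lesion "which was not imaged because of expired battery life (30 minutes"). The favorable accuracy figure is conditional: "For capsules that passed the pylorus and reached the duodenum, high-risk lesions were detected with a 95% sensitivity".
- **Section 2.1, passage rates.** "At 60 minutes, 98% of capsules visualize the duodenum"; with a 20-30 minute battery, "approximately 50% visualize the duodenum (12/25 [7], 44/83 [8], and 7/12 [14"]).

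**The concern.** The protocol names a result that means the test was not completed, but the rule that acts on the test does not use it. Nothing serious was seen on such a capsule, because the capsule never reached the region where it might have been seen. Under the literal wording the patient is discharged as if the capsule had been negative.

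Two things are at stake. One is safety: section 2.3.1 counts a missed high-risk lesion among the potential major adverse events, and the stated goal is safe discharge. The other is the meaning of the primary outcome. Percent Discharged Home pools discharges after a completed negative test with discharges after an incomplete one, and section 11.3 does not plan to report them separately.

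**Working it through.** **1. Does any rule cover the patient?** Take a capsule-arm patient whose capsule stayed in the stomach until the battery ran out, showed no lesion or blood, and who was stable for 4 hours.

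- Discharge sentence, step 11: every condition is met, so the patient goes home.
- Admission sentence, step 11: the VCE is neither Positive nor Negative under 3.2.2, so the sentence does not apply.
- Discretion, step 11: it covers only the 2-3 hemoglobin drop.
- Section 4.4, step 7: the coordinator watches pyloric passage live, but no consequence is attached.
- Section 18.9, item j: a record only.
- Section 11.3: an inadequate VCE is reclassified by EGD at analysis, after the patient has left.
- Section 5.2, exclusion 23: patients whose physician would not act on the VCE result are excluded, so informal override cannot be assumed.

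No other place gives a disposition. The mirror case is also uncovered: an Inconclusive VCE with instability fails the discharge sentence but is not named in the admission sentence.

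**2. How many patients?** Section 2.1 describes the capsule as filming for 30 minutes, and later relies on 60 minutes of viewing. Both are shown. The number in the capsule arm is not stated; 1:1 allocation of 100 gives an assumed 50.

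- 60 minutes: 1 − 0.98 = 2%; 0.02 × 50 = 1 patient.
- 20-30 minutes: not reaching the duodenum, 13/25, 39/83 and 5/12; pooled 57/120 = 47.5% (exact 95% CI 38.3% to 56.8%). Section 2.1 says that 1 of the 12 could not tolerate the capsule, so the 5 appears to include a patient with no completed test. Without that patient: (13 + 39 + 4)/(25 + 83 + 11) = 56/119 = 47.1%, and 0.471 × 50 ≈ 24 patients.

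Both shares overstate Inconclusive somewhat, because a non-passing capsule that shows a gastric or esophageal lesion is Positive. The second is a ceiling, since this trial also gives a prokinetic.

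**3. What would admitting them cost?** Section 11.2 expects at most 20% high-risk, so 0.80 × 50 = 40 low-risk patients.

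- If all 40 would otherwise go home: 40/50 = 80.0%. Admitting 2%: (40 − 0.8)/50 = 78.4%, a loss of 1.6 points.
- With the 92% specificity in section 2.1: 0.92 × 40 = 36.8, or 73.6%; then 36.8 × 0.98 = 36.1, or 72.1%, a loss of 1.5 points.

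**4. Power.** Section 11.2 claims at least 80% for a 25-point difference against 100% control admission. With 40 low-risk patients per arm, two-sided 0.05, I get 93.8% (normal approximation) or 95.7% (Fisher exact), so the claim holds. If low-risk patients are otherwise nearly all discharged, power stays above 99% even with 47.5% admitted as Inconclusive.

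**The case against.** **It is a drafting omission.** The three definitions stand under the secondary outcome, for sensitivity and specificity, and are not presented as triage categories. This stands in part. A reader might infer a deliberate policy of discharging on an incomplete test; the documents state no such policy. But step 11 borrows the words positive and negative, and its literal effect is discharge. If it is read as silent instead, the sites have no common rule.

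**The risk is contained.** A Glasgow-Blatchford score of 6 or more is excluded. A prokinetic is given, a trained gastroenterologist reviews each VCE, monitoring lasts 4 hours, patients are told to return if bleeding recurs, and EGD is booked within 3 days. At 2% non-passage, applying the 20% high-risk ceiling independently gives 1 × 0.20 = 0.2 high-risk patients. The feasibility trial in section 2.1 admitted 7 of 37 VCE patients with no difference in rebleeding or 30-day mortality. All this bears on severity. None of it distinguishes Inconclusive from Negative when discharge is decided, and section 2.1 does not say how that trial handled incomplete capsules.

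**The data exist and pooling is legitimate.** This largely stands. A reader might infer that discharges on a completed test cannot be identified. They can: the VCE form and videos are kept, and section 11.3 already requires inadequate VCEs to be recognized. A strategy outcome may also be pooled in a trial that calls itself pragmatic. What is missing is a pre-specified breakdown.

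**Conclusion.** The point holds and should be fixed. Step 11 leaves a defined test result without a disposition, and its literal wording sends home a stable patient with an unseen duodenum, the situation in which section 2.1 reports missed lesions.

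The size is uncertain: about 1 of an assumed 50 patients at 60 minutes of recording, and at most about 47% on the 20-30 minute experience. Two stronger inferences are not supported. The first is that about half the arm would be discharged on an incomplete test; that figure comes from earlier short-battery studies, and section 2.1 expects longer recording with a prokinetic to do better. The second is that admitting Inconclusive capsules would leave the trial underpowered. That would require treating the 25 points in section 11.2 as the expected effect before such admissions, whereas it is given as a detectable difference. The consequence lies in safety and in the meaning of the primary outcome, not in power.

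**What to change.** 1. **Step 11 of 4.4.** Discharge on capsule grounds requires a Negative VCE as defined in 3.2.2, plus 4 hours of stable hemoglobin, blood pressure and heart rate. By default, a stable Inconclusive VCE is admitted for inpatient EGD. If the sponsor prefers to send these patients home to the 3-day EGD, that should be written as a separate pathway, the same at every site.
2. **Section 11.3.** Pre-specify Percent Discharged Home overall and by VCE result (negative, inconclusive), with missed high-risk lesions and Day 7 and Day 30 events for each.
3. **Transition.** The document is dated 9/27/19, and section 6.2 plans recruitment from April 2018 to April 2019. If subjects are already enrolled, record which discharge rule applied to each, so that two rules are not mixed unseen in the primary outcome.

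The cost is a short amendment and one extra table. No new procedure is needed, because pyloric passage is already watched live and is known before the 4-hour decision. The downside is a lower discharge percentage: about 1.6 points at 2% inconclusive, and more if recording is shorter.
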